### 11.5.5 Other assessments

#### Corporate Confidential Information

Corporate Confidential Information

Corporate Confidential Information

### **11.7 Power for analysis of key secondary variables**

There are no power analyses for the secondary safety variables.

### **11.8 Interim analyses**

Corporate Confidential Information

---

## Corporate Confidential Information

## **12 Ethical considerations**

### **12.1 Regulatory and ethical compliance**

This clinical study was designed and shall be implemented and reported in accordance with the ICH Harmonized Tripartite Guidelines for Good Clinical Practice, with applicable local regulations (including European Directive 2001/20/EC, US Code of Federal Regulations Title 21, and Japanese Ministry of Health, Labor, and Welfare), and with the ethical principles laid down in the Declaration of Helsinki.

### **12.2 Responsibilities of the investigator and IRB/IEC**

Before initiating a trial, the investigator/institution should obtain approval/favorable opinion from the Institutional Review Board/Independent Ethics Committee (IRB/IEC) for the trial protocol, written informed consent form, consent form updates, subject recruitment procedures (e.g. advertisements) and any other written information to be provided to subjects. Prior to study start, the investigator is required to sign a protocol signature page confirming his/her agreement to conduct the study in accordance with these documents and all of the instructions and procedures found in this protocol and to give access to all relevant data and records to Novartis monitors, auditors, Novartis Quality Assurance representatives, designated agents of Novartis, IRBs/IECs, and regulatory authorities as required. If an inspection of the clinical site is requested by a regulatory authority, the investigator must inform Novartis immediately that this request has been made.

For multi-center trials, a Coordinating Investigator will be selected by Novartis around the time of Last Patient Last Visit to be a reviewer and signatory for the clinical study report.

## **12.3 Publication of study protocol and results**

Novartis assures that the key design elements of this protocol will be posted in a publicly accessible database such as clinicaltrials.gov. In addition, upon study completion and finalization of the study report the results of this trial will be either submitted for publication and/or posted in a publicly accessible database of clinical trial results.

## **13 Protocol adherence**

This protocol defines the study objectives, the study procedures and the data to be collected on study participants. Additional assessments required to ensure safety of subjects should be administered as deemed necessary on a case by case basis. Under no circumstances should an investigator collect additional data or conduct any additional procedures for any research related purpose involving any investigational drugs.

Investigators must apply due diligence to avoid protocol deviations. If the investigator feels a protocol deviation would improve the conduct of the study this must be considered a protocol amendment, and unless such an amendment is agreed upon by Novartis and approved by the IRB/IEC/REB it cannot be implemented. All significant protocol deviations will be recorded and reported in the CSR.

### **13.1 Protocol Amendments**

Any change or addition to the protocol can only be made in a written protocol amendment that must be approved by Novartis, Health Authorities where required, and the IRB/IEC prior to implementation.

Only amendments that are intended to eliminate an apparent immediate hazard to subjects may be implemented, provided the Health Authorities and the reviewing IRB/IEC are subsequently notified by protocol amendment.

Notwithstanding the need for approval of formal protocol amendments, the investigator is expected to take any immediate action required for the safety of any subject included in this study, even if this action represents a deviation from the protocol. In such cases, the CTL should be informed and (serious) adverse event reporting requirements ([Section 9](#)) followed as appropriate.

1.1 Scope

The RAP documents contain detailed information to aid the production of Statistics & Programming input into the Clinical Study Report (CSR) for trial "CLHW090X2202".

The Statistical analysis plan (SAP) describes the implementation of the statistical analysis planned in the protocol.

2 Study objectives and design

2.1 Study objectives

2.1.1 Primary objectives

- To assess the safety and tolerability of LHW090 for 4 weeks on a background of conventional anti-hypertensive medications in patients with resistant hypertension.
- To evaluate the effect of LHW090 on placebo-adjusted mean daytime systolic blood pressure (SBP) after 4 weeks in patients with resistant hypertension.

2.1.2 Secondary objective

• To evaluate the pharmacokinetics (PK) of LHW090 and its active metabolite LHV527 in patients with resistant hypertension.

2.1.3 Exploratory objectives

Corporate Confidential Information

[figure not shown]
2.2 Study design and treatment

This is a non-confirmatory, randomized, sponsor open, site and subject blind, parallel group, placebo-controlled study to evaluate the safety and efficacy of 4 weeks once daily treatment with LHW090 in patients with resistant hypertension. Patients with uncontrolled hypertension as defined as a mean daytime systolic blood pressure ≥ 135 mmHg by ambulatory blood pressure monitoring (ABPM) on a stable (at least 2 months) regimen of an angiotensin receptor blocker (ARB) plus a thiazide diuretic plus at least one of the following commonly used classes of anti-hypertensive medications—beta-blockers or calcium channel blockers—will be considered for this trial. Patients with resistant hypertension will be randomized to

either placebo or 1 of 2 dose regimens of LHW090, i.e. LHW090 100 mg once daily or LHW090 200 mg once daily, as an add-on to their anti-hypertensive regimen at baseline.

Each patient will participate in an up to 3 week screening period, a 2-week single blind placebo run-in period, baseline assessments, a 4 week treatment period, and an end of study assessment as demonstrated in Figure 2-1. During the 2 week placebo run-in period, patients will receive regular reminders by the site to be compliant with their anti-hypertensive medications. At the end of this run-in period, patients who demonstrate \geq 80% compliance with placebo will be randomized. Compliance will be established by pill count and review of medication diary. Patients will be advised that study entry cannot be fully determined until the completion of the run-in period.

Figure 2-1 Study design

Approximately a total of 80 patients to be randomized in the study: Placebo (n~40), LHW090 100 mg (n~20), LHW090 200 mg (n~20)

▼Interim analysis

3 First interpretable results (FIR)

First interpretable results (FIR) will be provided for this trial.

The study FIR template (mock slides) can be found in CREDI in the study RAP folder.

The template shows the analysis / results to be presented in the FIR. Study outputs required to be created at the time of the FIR will be highlighted in the TFL shells document and marked as "Key" in the Tracking sheet output list.

4 Interim analyses

[&]quot;Up to 25 days allowed for screening, but patient may proceed to run-in phase at any time once all screening requirements have been met

5 Statistical methods: Analysis sets

For subjects for which the actual treatment received does not match the randomized treatment the treatment actually received will be used for the analysis.

All subjects that were randomized will be included in the safety analysis set.

The PK analysis set will include all subjects with at least one available valid (i.e. not flagged for exclusion) PK concentration measurement, who received any study drug and experienced no protocol deviations with relevant impact on PK data.

The primary PD analysis set will include all subjects that received any study drug, with any available post-dose PD data.

The secondary PD analysis set will include all subjects that received any study drug, with any available post-dose PD data and experienced no protocol deviations with relevant impact on PD data.

The analysis sets and protocol deviation codes are related as follows:

Table 5-1 Protocol deviation severity codes and analysis sets

Protocol deviation severity code		Safety analysis set	PK analysis set	PD analysis set	Secondary PD analysis set
Code	Text				
5	Exclude subject from all safety analysis	-	-	-	-
8	Exclude from all analyses	-	-	-	-
20	Exclude subject from PK analysis set	+	-	+	+
22	Exclude subject from PD analysis set	+	+	-	-
23	Exclude subject from PK and PD analysis set	+	-	-	-
49	Report relevant protocol deviation – include subject in all analysis sets	+	+	+	+

^{+ =} include in analysis set, - = exclude from analysis set, NA = not applicable

6 Statistical methods for Pharmacokinetic (PK) parameters

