## 2 Study objectives

### 2.1 Primary objective(s)

Objective	Endpoint

To assess the safety and tolerability of LHW090 for 4 weeks on a background of conventional anti-hypertensive medications in patients with resistant hypertension.

	

Safety endpoints (adverse events, serious adverse events) up to and including end of study assessments

To evaluate the effect of LHW090 on placebo-adjusted mean daytime systolic blood pressure (SBP) after 4 weeks in patients with resistant hypertension.

	

Change from baseline daytime SBP on week 4 by Ambulatory blood pressure monitoring

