### **11.1 Analysis sets**

For all analysis sets, subjects will be analyzed according to the study treatment(s) received.

The full analysis set will include all subjects who received study treatment.

The safety analysis set will include all subjects that received any study drug.

The PK analysis set will include all subjects with available PK data and no protocol deviations with relevant impact on PK data.

The primary PD analysis set will include all subjects with available PD data. The secondary PD analysis set will include all subjects with available PD data and no protocol deviations with relevant impact on PD data.

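### The SAP defines the safety set as all randomised subjects where the protocol requires dosing, and its deviation codes 5 and 8 can remove subjects from that set without a stated limit

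*SAP*

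**What the plan says.** Protocol 11.1 bases the safety set on exposure: "The safety analysis set will include all subjects that received any study drug". It attaches no deviation exclusion to that set, although it does attach one to the PK set and to the secondary PD set. It also fixes the grouping: "For all analysis sets, subjects will be analyzed according to the study treatment(s) received".

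SAP section 5 bases the set on randomisation: "All subjects that were randomized will be included in the safety analysis set". It adds no dosing condition, yet the PK set and both PD sets in the same section each require that study drug was received. Where actual and randomised treatment differ, "the treatment actually received will be used for the analysis".

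SAP Table 5-1 then links deviation codes to sets. Code 5 reads "Exclude subject from all safety analysis" and code 8 reads "Exclude from all analyses". Both carry a minus sign in the safety column, and the table key defines a minus as "exclude from analysis set". Codes 20, 22, 23 and 49 all carry a plus for safety.

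The first primary objective in protocol 2.1 is "To assess the safety and tolerability of LHW090 for 4 weeks on a background of conventional anti-hypertensive medications in patients with resistant hypertension". SAP 7.1 likewise names adverse events, vital signs, ECG intervals and laboratory values as the first primary variables.

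**The concern.** SAP 1.1 presents the SAP as implementing the analysis planned in the protocol. On this point it changes the population for a primary objective and does not say so.

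Two consequences follow if the SAP is applied literally. First, a subject who is randomised but never takes a dose enters the safety set. That subject has no treatment received, so the column of the adverse event table in which they belong is undefined. In whichever column they are placed, they enlarge the denominator without having been exposed. Second, a dosed subject who is given code 5 or 8 leaves the safety set, which the protocol definition does not permit.

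SAP 7.1.3 makes the safety analysis descriptive, and SAP 8.1.2 reports counts and percentages of subjects with events by treatment. No model or test stands behind those percentages, so set membership determines both numerator and denominator.

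**Working it through.** **Step 1. The rules side by side.**

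| Subject | Protocol 11.1 | SAP 5, sentence | SAP Table 5-1 |
|---|---|---|---|
| Randomised, dosed, no deviation | in | in | no code applies |
| Randomised, never dosed | out | in | out only if coded 5 or 8; no visible text requires that |
| Randomised, dosed, code 20, 22, 23 or 49 | in | in | in |
| Randomised, dosed, code 5 or 8 | in | in | out |

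The documents disagree in the second and fourth rows.

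**Step 2. Can the second row occur?** Protocol 6.4 and footnote 15 of Table 8-1 place randomisation before the first dose. A randomised, undosed subject is therefore possible. The documents do not say how many to expect.

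**Step 3. Can the fourth row occur?** No visible text says which deviations receive code 5 or 8, or confines them to undosed subjects. The table therefore permits it. The documents do not show that it would happen.

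**Step 4. Size.** The plan states no figure to reproduce. The planned arm sizes are 40 on placebo and 20 on each dose (protocol 11.4.2). The numbers of subjects with events, undosed subjects and removed subjects below are assumptions chosen for illustration.

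Let *n* be the number randomised to an arm and *e* the number of subjects with an event.

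(a) *u* undosed subjects, none with an event. The protocol rate is e/(n − u) and the SAP rate is e/n.

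- n = 20, e = 6, u = 1: 6/19 = 31.6% against 6/20 = 30.0%, a fall of 1.6 points.
- n = 20, e = 6, u = 2: 6/18 = 33.3% against 30.0%, a fall of 3.3 points.
- n = 20, e = 2, u = 1: 2/19 = 10.5% against 2/20 = 10.0%, a fall of 0.5 points.
- n = 40, e = 12, u = 1 or 2: 12/39 = 30.8% or 12/38 = 31.6%, against 12/40 = 30.0%.

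(b) All *n* dosed, and *x* subjects with an event removed by code 5 or 8. The protocol rate is e/n and the SAP rate is (e − x)/(n − x).

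- n = 20, e = 6, x = 1: 30.0% against 5/19 = 26.3%, a fall of 3.7 points.
- n = 20, e = 6, x = 2: 30.0% against 4/18 = 22.2%, a fall of 7.8 points.
- n = 20, e = 2, x = 1: 10.0% against 1/19 = 5.3%, a fall of 4.7 points.
- n = 20, e = 1, x = 1: 1/20 = 5.0% against 0/19 = 0%, a fall of 5.0 points.
- n = 40, e = 12, x = 1 or 2: 30.0% against 11/39 = 28.2% or 10/38 = 26.3%.

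Removing a dosed subject without an event moves the rate up instead: with n = 20 and e = 6, from 30.0% to 6/19 = 31.6%.

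(c) With u = 0 and x = 0 the two sets are the same and the difference is zero.

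**The case against.** The strongest reply is that the sets may well coincide. Randomisation takes place once eligibility is confirmed, and doses on visit days are taken at the site (protocol 3.1), so few or no subjects should be randomised and left undosed. A general sentence followed by a table of exceptions is also ordinary SAP structure. Code 5 removes the subject from the PK and PD sets as well as from safety, which fits a code meant for people who were never dosed or have no usable data. On that reading, all randomised subjects less those coded 5 comes close to the protocol set. The mapping of deviations to codes may also sit in another of the analysis-plan documents that SAP 1.1 mentions. This limits the likely size and makes a benign intent plausible. It does not change what the SAP sentence says, and the visible text does not state the benign reading.

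Three stronger readings are tempting, and the documents do not support them.

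- *Harmed patients would be deleted.* A reader might infer that a dosed patient with a serious event and a protocol deviation would disappear from the safety tables. Codes 20, 22, 23 and 49 all keep the subject in the safety set, and a patient who took a prohibited drug fits one of those at least as well as 5 or 8.
- *The sponsor-open design makes the coding biased.* Protocol 10.2 has deviations determined and the database locked before treatment codes are released for analysis, and protocol 6.5 restricts the randomisation data to authorised personnel. Sponsor-open status leaves some risk, but nothing shows that whoever assigns the codes knows the treatment.
- *Run-in placebo counts as study drug.* A reader might infer that run-in failures qualify under protocol 11.1. Protocol 6.2 defines the study treatments as the three assigned arms and 11.1 groups subjects by treatment received, so a run-in failure has no group. That reading is strained.

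**Conclusion.** The SAP sentence is wrong as written: it sets a different safety population from protocol 11.1, and it admits subjects whom the rule of analysis by treatment received cannot place. Table 5-1 adds a second, lesser fault. The minus signs for codes 5 and 8 are not wrong in themselves, but nothing visible limits them to subjects who were never dosed or whose data may not be used.

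The conclusion about the text needs no assumption. The size does. The effect is nil if every randomised subject is dosed and neither code is used. If not, one subject is about 5 percentage points of an active arm of 20. In the illustrative cases, one undosed subject lowers the rate in such an arm by 0.5 to 1.6 points, and removing one subject with an event lowers it by 3.7 to 5.0 points. The documents supply no counts for either situation. Sample size, power and the efficacy test are untouched.

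**What to change.** 1. In SAP section 5, replace the safety-set sentence with: *The safety analysis set includes all subjects who received at least one dose of randomised study treatment (LHW090 or placebo, from and including the Day 1 dose), analysed by treatment received.* The Day 1 dose must be expressly included, so that a patient who stops after the first dose stays in. This wording also settles that run-in placebo alone does not qualify.
2. In Table 5-1, limit codes 5 and 8 to subjects who never received randomised treatment or whose data may not be used at all (for example, no valid consent). Add that no other protocol deviation removes a dosed subject from the safety set.
3. List randomised but undosed subjects separately, with any events they had.

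The cost is one SAP sentence, a definition for each of two codes and one listing, all before database lock. No new data are needed.

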## 8.3 Efficacy / Pharmacodynamics

Pharmacodynamic assessments are specified below, with the methods for assessment and recording specified in the Study Operations Manual. Assessments will be performed/samples collected at the timepoint(s) defined in the [Assessment schedule](#).

In order to better define the PD profile, the timing of the sample collection may be altered based on emergent data. The number of samples/blood draws and total blood volume collected will not exceed those stated in the protocol. The results need to remain blinded during the study.

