7.1 Analysis of the primary variables

The first primary variables are adverse events, vital signs (blood pressure, pulse rate, body temperature), ECG intervals and laboratory measurements.

The second primary variable will be the change in the 12 hour average of SBP measured by ABPM 28 days following the start of treatment.

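### Codes 22 and 23 in SAP Table 5-1 remove from the primary PD set subjects whom SAP section 5 and protocol 11.1 keep in it

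*SAP*

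**What the plan says.** Protocol 11.1 defines the PD sets as a pair. For the first: "The primary PD analysis set will include all subjects with available PD data". For the second: "The secondary PD analysis set will include all subjects with available PD data and no protocol deviations with relevant impact on PD data".

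SAP section 5 keeps the same distinction and adds a dosing requirement. Its primary definition reads: "The primary PD analysis set will include all subjects that received any study drug, with any available post-dose PD data". Its secondary definition repeats this and adds the absence of PD-relevant deviations.

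Table 5-1 follows directly and is introduced as relating deviation codes to the analysis sets. Its third column is headed for the PD set, without the word primary; its fourth is headed for the secondary PD set. Two codes are specific to PD. Code 22 is labelled "Exclude subject from PD analysis set" and code 23 "Exclude subject from PK and PD analysis set". Both carry a minus in the third and the fourth column.

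On safety, protocol 11.1 limits the set to dosed subjects. SAP section 5 places everyone randomised in it, yet Table 5-1 gives codes 5 and 8 a minus in the safety column.

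**The concern.** The two PD sets are meant to differ in one respect: subjects with a PD-relevant deviation stay in the primary set and leave the secondary set. The table is the operational rule by which a coded deviation becomes an exclusion. If it gives the same answer for both sets, a programmer working from the table and one working from the definitions will build different primary PD sets from the same data. Following the table discards observed PD data that the definition retains.

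**Working it through.** No figure in the plan has to be reproduced; this is a check of set logic. The inputs are the six rows of SAP Table 5-1 and the definitions in SAP section 5 and protocol 11.1.

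**Step 1. Compare the two PD columns row by row.**

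| Code | Safety | PK | PD | Secondary PD | PD columns equal? |
|---|---|---|---|---|---|
| 5 | − | − | − | − | yes |
| 8 | − | − | − | − | yes |
| 20 | + | − | + | + | yes |
| 22 | + | + | − | − | yes |
| 23 | + | − | − | − | yes |
| 49 | + | + | + | + | yes |

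The columns are equal in 6 of 6 rows.

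**Step 2. Ask what would separate the sets.** By definition the secondary set lies within the primary set, so the only separating pattern is plus for primary and minus for secondary. It occurs in 0 of 6 rows.

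**Step 3. Allow several codes per subject.** Six codes give 2^6 = 64 combinations, counting the empty one. If a subject leaves a set when any code carries a minus for it, 0 of 64 combinations separate the two sets. That follows from step 1, since identical columns give identical exclusions.

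**Step 4. Locate the conflict with the text.** Codes 5 and 8 are general exclusions, code 20 concerns PK only, and code 49 excludes from nothing. The PD-specific conflict is therefore in two cells: the third column for codes 22 and 23. Both should be plus if the text governs.

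**Step 5. Express the difference in set size.** Let N dosed subjects have post-dose PD data, and let k of them carry code 22 or 23 and no general exclusion code.

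- Text: primary N, secondary N − k.
- Table: primary N − k, secondary N − k.

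The documents give no value for k. Purely as an illustration, take N as the completers expected in protocol 11.4.2, 32 + 16 + 16 = 64, and assume k = 2, 4 or 8. The text then gives 64/62, 64/60 and 64/56 (primary/secondary). The table gives 62/62, 60/60 and 56/56.

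**Step 6. Repeat after the correction.** With code 22 as + + + − and code 23 as + − + −, the PD columns differ in 2 of 6 rows. The separating combinations are those with neither 5 nor 8, at least one of 22 and 23 (3 ways), and any choice on 20 and 49 (2 × 2 = 4 ways): 3 × 4 = 12 of 64.

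**The case against.** The table is consistent within itself: the labels of codes 22 and 23 agree with their cells, and the visible SAP does not say whether table or text prevails. Both sets are fully defined in words just above the table, so a careful programmer could build them without it. If no subject receives code 22 or 23, nothing changes; with no PD-relevant deviations the text also yields identical sets. The study is described as non-confirmatory.

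These points limit the consequence but do not remove the conflict. Protocol 11.1 agrees with the SAP text against the table, which is good reason to take the text as intended. Reading the third column as a generic PD set does not help, because the primary set would then have no column and there would still be no code for the secondary set alone.

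A reader might infer that the primary ABPM result is affected. Protocol 8.3 does open its efficacy section with "Pharmacodynamic assessments are specified below", and SAP 7.1, within the PD chapter, states "The second primary variable will be the change in the 12 hour average of SBP measured by ABPM". But a chapter heading does not assign an analysis set. Protocol 11.1 also offers another candidate, "The full analysis set will include all subjects who received study treatment", and the relevant text may be redacted or not visible. A reader might likewise infer that a planned comparison of the two PD sets is lost; no visible section plans one.

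On the smaller items, the two safety definitions differ only for subjects randomised but never dosed, and Table 5-1 can be read as qualifying the general sentence on the safety set. Both are fair, which is why those items are minor.

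**Conclusion.** The mismatch is certain on the visible text: identical PD columns in 6 of 6 rows, no code specific to the secondary set, and two cells that contradict the primary PD definition in both documents. All table signs are legible, and no redacted text is needed to see the conflict. It takes effect only where code 22 or 23 is used, and then each affected subject with PD data is wrongly dropped from the primary PD set. This should be fixed.

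The conclusion rests on reading the third column as the primary PD set, the natural reading since it is the only other PD column. It does not extend to the primary efficacy result: the visible text does not establish which set that analysis uses, and the documents fix neither the size nor the direction of any effect.

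Two minor points stand beside it. The SAP safety set (all randomised) departs from protocol 11.1 (dosed subjects). Codes 5 and 8 exclude subjects from a set whose definition admits no exclusion. Protocol 6.4 places randomisation before dosing, so a randomised but undosed subject is possible.

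**What to change.** In SAP Table 5-1:

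- Head the third column *Primary PD analysis set*.
- Set that column to plus for codes 22 and 23; leave the secondary PD column at minus.
- Relabel code 22 as excluding from the secondary PD set, and code 23 as excluding from the PK and secondary PD sets.
- Before database lock, re-check every deviation already coded 22 or 23 against the new meaning.

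If the sponsor prefers not to redefine codes that may already be assigned, a new code specific to the secondary PD set would also work. The primary PD definition would then have to state which deviations codes 22 and 23 remove.

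Minor, in the same revision: align the SAP safety set with protocol 11.1, and state when, if ever, codes 5 and 8 may remove a subject from it.

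The main fix costs two cells, two labels, one column heading and the re-check. The minor items cost one changed definition and one clarifying sentence. No protocol amendment and no new data are needed.
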